12.4.4.3 Electrocardiogram

A summary of raw values and change from baseline values at each visit will be provided for current dosing period based on Study 110 Safety Set, and for the active dosing period based on the Integrated Safety Set for the following standard digital ECG measurements: PR, QT, QTc intervals, QRS, and HR. Mean QTcF values will be plotted against visit.

For subjects with at least 1 PCS event during the treatment-emergent period, the number and percentage of subjects with PCS per 100 patient-year (number of PCS adjusted for the total duration of exposure) will be tabulated. The PCS criteria will be provided in the SAP.

A listing of subjects with PCS events during the treatment-emergent period will be presented, including all parameters and assessments at all visits.

The number and percentage of subjects with shift changes from baseline, based on the worst on-treatment overall ECG evaluation, will be tabulated.

12.4.4.4 Vital Signs

A summary of raw values, and change from baseline values at each visit, will be provided for current dosing period based on Study 110 Safety Set, and for the active dosing period based on the Integrated Safety Set for the following vital signs variables: systolic and diastolic blood pressure (mm Hg), body temperature (°C), HR (beats per minute), and respiratory rate (breaths per minute).

For subjects with at least 1 PCS event during the treatment-emergent period, the number and percentage of subjects and number of PCS per 100 patient-year (number of PCS adjusted for the total duration of exposure) will be tabulated. The PCS criteria will be provided in the SAP. A listing of subjects with PCS events during the treatment-emergent period will be presented, including all parameters and assessments at all visits.

The number and percentage of subjects with shift changes from baseline (normal/missing, high, or low according to the reference range) based on the worst on-treatment vital signs evaluation will be tabulated.

12.4.4.5 Pulse Oximetry

For the pulse oximetry measurements, a summary of raw values and change from baseline values will be provided for current dosing period based on Study 110 Safety Set, and for the active dosing period based on the Integrated Safety Set at each scheduled time point for the percent of oxygen saturation by pulse oximetry. In addition, the mean value at each visit will be plotted for the percent of oxygen saturation.

The number and percentage of subjects with shift changes from baseline (normal/missing and low according to the reference range) to the lowest percent of oxygen saturation during the treatment-emergent period will be tabulated based on the Safety Set.

12.4.4.6 Ophthalmological examinations

For the analysis of slit lamp lens, the number and percentage of subjects with shift changes from baseline (normal versus abnormal) will be tabulated for the current dosing period based on Study 110 Safety Set, and active dosing period based on the Integrated Safety Set at each scheduled time point. Ophthalmological examination findings will be presented as a data listing.

12.4.4.7 Spirometry

Analysis of Predose Spirometry at Each Postdose Visit

Spirometry data will be summarized descriptively for the predose assessment at each postdose visit, for the current dosing period based on Study 110 Safety Set, and the active dosing period separately, based on the Integrated Safety Set:

- Number and percentage of subjects with ≥ 5 percentage points decrease, or ≥ 10 percentage points decrease in absolute change from baseline in ppFEV₁ at each visit
- Number and percentage of subjects with $\geq 5\%$ decrease, or $\geq 10\%$ decrease in relative change from baseline in ppFEV₁ at each visit
- Number and percentage of subjects with ≥ 0.05 L decrease, or ≥ 0.10 L decrease in absolute change from baseline in FEV₁ at each visit
- Number and percentage of subjects with $\geq 5\%$ decrease, or $\geq 10\%$ decrease in relative change from baseline in FEV₁ at each visit

Subjects with ≥ 5 percentage points decrease in absolute change from baseline in ppFEV₁ or ≥ 0.05 L absolute change from baseline in FEV₁ at any visit will be listed. The listing will include raw values and absolute/relative changes from baseline in ppFEV₁ and FEV₁ at all visits.

Analysis of Serial Spirometry

Based on the Integrated Safety Set for the active dosing period and based on the Study 110 Safety Set for the current dosing period, raw values and absolute change from predose assessment in ppFEV₁ and FEV₁ will be summarized by visit and by time point:

The mean values (95% CI) will be plotted against visit and time points. The number and percentage of subjects with a decline ≥ 5 , ≥ 10 , ≥ 15 , and ≥ 20 percentage points in the absolute change from the predose value in ppFEV₁ will be summarized by visit and time point.

12.4.4.8 Physical Examination

PE findings will be presented as a data listing.

12.4.4.9 Other Safety Analysis

Not applicable

12.4.5 Interim and IDMC Analyses

12.4.5.1 Interim Analysis

One interim analysis (IA) will be conducted for the Treatment Cohort when all subjects have completed the Week 24 Visit. Details of the analyses will be described in the IA SAP.

Additional IAs may take place at any other time during the study if (1) warranted by the ongoing data, (2) needed for regulatory purposes, and/or (3) deemed necessary by the internal Vertex team.

12.4.5.2 IDMC Analysis

Details of the IDMC (Section 8.1.4) analysis will be provided in the IDMC Analysis Plan.

13 PROCEDURAL, ETHICAL, REGULATORY, AND ADMINISTRATIVE CONSIDERATIONS

13.1 Adverse Event and Serious Adverse Event Documentation, Severity Grading, and Reporting

13.1.1 Adverse Events

13.1.1.1 Definition of an Adverse Event

An AE is defined as any untoward medical occurrence in a subject during the study; the event does not necessarily have a causal relationship with the treatment. This includes any newly occurring event or worsening of a pre-existing condition (e.g., increase in its severity or frequency) after the ICF is signed.

An AE is considered serious if it meets the definition in Section 13.1.2.1.

13.1.1.2 Clinically Significant Assessments

Study assessments including laboratory tests, ECGs, PEs, and vital signs, will be assessed and those deemed a clinically significant worsening from baseline documented as an AE. When possible, a clinical diagnosis for the study assessment will be provided, rather than the abnormal test result alone (e.g., urinary tract infection, anemia). In the absence of a diagnosis, the abnormal study assessment itself will be listed as the AE (e.g., bacteria in urine or decreased hemoglobin).

An abnormal study assessment is considered clinically significant if the subject has 1 or more of the following:

- Concomitant signs or symptoms related to the abnormal study assessment
- Further diagnostic testing or medical/surgical intervention
- A change in the dose of study drug or discontinuation from the study

Repeat testing to determine whether the result is abnormal, in the absence of any of the above criteria, does not necessarily meet clinically significant criteria. The determination of whether the study assessment results are clinically significant will be made by the investigator.

A laboratory value that is Grade 4 will not automatically be an SAE. A Grade 4 laboratory value will be an SAE if the clinical status of the subject indicates a life-threatening AE.

13.1.1.3 Documentation of Adverse Events

All ongoing or newly developed AEs at, or after, completion of treatment in Study 109 or Study 011B will be collected until the following time points:

- Withdrawal of consent or through the Safety Follow-up Visit (NOTE: only SAEs will be collected for the Observational Cohort)
- For enrolled subjects who do not have a Safety Follow-up Visit: 28 days after the last dose of study drug

All subjects will be queried, using non-leading questions, about the occurrence of AEs at each study visit. When possible, a constellation of signs and/or symptoms will be identified as 1 overall event or diagnosis. All AEs for enrolled subjects will be recorded in the eCRF and source document. The following data will be documented for each AE:

- Description of the event
- Classification of “serious” or “nonserious”
- Date of first occurrence and date of resolution (if applicable)
- Severity
- Causal relationship to study drug(s)
- Action taken
- Outcome
- Concomitant medication or other treatment given

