Table 3-2 Study VX15-809-110: Observational Cohort

Event/Assessment	Day 1 ^a	Long-term Follow-up	
		Approximately Every 3 to 4 Months for the First Year	Approximately 2 Years (± 4 weeks)
Clinic visit	X		
Telephone contact		X	X
Informed consent/assent	X		
Inclusion criteria review	X		
Serious adverse events	Continuous, from signing of ICF (and assent form, if applicable) through the last telephone contact		

ICF: informed consent form.

^a The Day 1 Visit of Study 110 will be on the **same day** as the Week 24 Visit (last Treatment Period visit) of Study 109 or the Week 26 Visit (Safety Follow-up Visit) of Study 011B for subjects at Study 110 sites that have been activated by the time the Week 24 Visit (Study 109) or the Week 26 Visit (Study 011B) has been completed. Subjects at these active sites will NOT have to repeat any Study 110 Day 1 assessments that were specified to be performed at the Week 24 Visit (Study 109) or the Week 26 Visit (Study 011B). The Day 1 Visit of Study 110 **will NOT coincide** with the Week 24 Visit (last Treatment Period visit) of Study 109 or the Week 26 Visit (Safety Follow-up Visit) of Study 011B for subjects at Study 110 sites that have NOT been activated by the time the Week 24 Visit (Study 109) or the Week 26 Visit (Study 011B) has been completed. Subjects at these nonactive sites will have to repeat any Study 110 Day 1 assessments (in addition to completing Study 110-specific Day 1 events/assessments) that were specified to be performed at the Week 24 Visit (Study 109) or the Week 26 Visit (Study 011B).

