7.2 Secondary Endpoints

Treatment Cohort

The following efficacy endpoints will be analyzed using baseline values in the previous study (i.e., Study VX14-809-109 [Study 109], Study VX13-809-011B [Study 011B], or Study VX13-809-011B Lung Clearance Index [LCI] Substudy [Study 011B LCI Substudy]):

- Absolute change from baseline in LCI_{2.5} (subjects from Study 109 and the Study 011B LCI Substudy only)
- Absolute change from baseline in sweat chloride
- Absolute change from baseline in body mass index (BMI)
- Absolute change from baseline in Cystic Fibrosis Questionnaire-Revised (CFQ-R) respiratory domain score

The following efficacy endpoints will be analyzed using baseline values in the current study (Study VX15-809-110 [Study 110]):

- Absolute change from baseline in LCI_{2.5} (subjects from Study 109 and the Study 011B LCI Substudy only)
- Absolute change from baseline in sweat chloride
- Absolute change from baseline in BMI
- Absolute change from baseline in CFQ-R respiratory domain score

Observational Cohort

Safety, as determined by serious adverse events (SAEs)

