The following subjects from Study 109 or Study 011B who meet the study criteria (Section 9.1) and elect to enroll in Study 110 are eligible for enrollment in the Observational Cohort:

- Subjects who received at least 4 weeks of study drug in Study 109 or Study 011B and completed visits up to Week 24 of Study 109 or Week 26 of Study 011B but who are not eligible (Sections 9.1 and 9.2) for the Treatment Cohort with lumacaftor in combination with ivacaftor
- Subjects who received at least 4 weeks of study drug in Study 109 or Study 011B (and did not prematurely discontinue study drug treatment) and completed visits up to Week 24 of Study 109 or Week 26 of Study 011B but who elect not to continue treatment with lumacaftor in combination with ivacaftor

Subjects in the Observational Cohort will not receive study drug and will have regularly scheduled telephone calls for approximately 2 years after their last dose of study drug in Study 109 or Study 011B to assess the post-treatment safety of lumacaftor and ivacaftor combination therapy.

Figure 8-1 Schematic of Study Design

IVA: ivacaftor; LUM: lumacaftor; q12h: every 12 hours.

- ^a The following subjects may be eligible for enrollment in the Treatment Cohort: (1) subjects who completed 24 weeks of study drug treatment (i.e., lumacaftor in combination with ivacaftor or placebo) in Study 109 or completed 24 weeks of study drug treatment and the Week 26 Safety Follow-up in Study 011B (NOTE: the last dose of study drug is the evening dose administered the day before the Week 24 Visit or the dose at the Week 24 Visit [based on the applicable protocol version for which a subject screens (provides consent/assent) under] in Study 109 or the evening dose administered the day before the Week 24 Visit in Study 011B) and (2) subjects who are not receiving study drug treatment at the end of the Treatment Period in Study 109 or Study 011B (NOTE: subjects from Study 011B have a planned Washout Period from Week 24 to Week 26 and must still complete the Week 26 Safety Follow-up), including subjects that require study drug interruption to be either continued or initiated at Day 1 in Study 110, AND who have received Vertex approval for entry. Subjects who prematurely discontinued study drug treatment are not eligible for enrollment in the Treatment Cohort.

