8.1.1.2 Follow-up

The Safety Follow-up Visit is scheduled to occur 4 weeks (\pm 7 days) after the last dose of study drug for subjects in the Treatment Cohort. Safety Follow-up Visit assessments are listed in [Table 3-1](#).

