8.1.2.2 Long-term Follow-up

Subjects in the Observational Cohort will be followed for approximately 2 years. A telephone contact will be made every 3 to 4 months during the first year and at approximately 2 years (\pm 4 weeks) as shown in [Table 3-2](#).

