13.1.2.2 Documentation of Serious Adverse Events

All SAEs that occur after obtaining informed consent and assent (where applicable) through the Follow-up Visit, regardless of causality, will be reported by the investigator to Vertex GPS. In addition, all SAEs that occur after the study has concluded and are considered related to study drug(s) will be reported to Vertex GPS **within 24 hours**.

SAEs will be recorded on the Vertex Organized Safety Information Collection Form (hereafter referred to as the “SAE Form”) using a recognized medical term or diagnosis that accurately reflects the event. SAEs will be assessed by the investigator for relationship to the investigational study drug(s) and possible etiologies. On the Clinical Trials SAE Form, relationship to study drug(s) will be assessed only as related (includes possibly related) or not related (includes unlikely related), and severity assessment will not be required. For the purposes of study analysis, if the event has not resolved at the end of the study reporting period, it will be documented as ongoing. For purposes of regulatory safety monitoring, the investigator is required to follow the event to resolution and report to Vertex the outcome of the event using the Vertex Clinical Trials SAE Form.

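### Section 13.1.1.3 of the protocol contradicts the Observational Cohort's own schedule on when SAE collection ends

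*Protocol*

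**What the plan says.** Section 13.1.1.3 gives two end points for collecting events. The first is withdrawal of consent or the Safety Follow-up Visit, with a note that "only SAEs will be collected for the Observational Cohort". The second reads: "For enrolled subjects who do not have a Safety Follow-up Visit: 28 days after the last dose of study drug". Neither bullet states an end point specific to the Observational Cohort.

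Section 8.1.1.2 schedules the Safety Follow-up Visit 4 weeks "after the last dose of study drug for subjects in the Treatment Cohort". Table 3-2 gives the Observational Cohort a Day 1 clinic visit and then telephone contacts only.

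On SAEs, Table 3-2 says: "Continuous, from signing of ICF (and assent form, if applicable) through the last telephone contact". SAP Table 13-3 repeats this. Section 8.1 promises "regularly scheduled telephone calls for approximately 2 years after their last dose of study drug in Study 109 or Study 011B". Section 8.1.2.2 adds the timing: "A telephone contact will be made every 3 to 4 months during the first year", with a final contact at about 2 years (± 4 weeks).

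Section 13.1.2.2 has SAEs from consent "through the Follow-up Visit, regardless of causality, will be reported by the investigator to Vertex GPS". Once the study has concluded, it asks only for SAEs considered related to study drug.

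**The concern.** SAEs are the only endpoint of the Observational Cohort (Section 7.2) and the whole basis of the secondary objective on post-treatment safety (Section 6.2). The protocol gives two incompatible answers to when their collection stops. Section 11.7.1 sends sites to Section 13.1 for collection periods, so a site has textual grounds for following 13.1.1.3 rather than Table 3-2. We found no statement of which prevails.

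If sites differ, the SAE output (a summary table in Protocol 12.4.4.1, a listing in SAP 10.4.1) would combine children followed for SAEs for a few weeks with children followed for about 2 years. The planned outputs would not reveal this. The disposition summary counts completed telephone contacts, and a child can complete every call at a site that has stopped recording SAEs.

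**Working it through.** No sample size or power figure bears on this point. The check is a comparison of passages followed by date arithmetic.

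**Step 1: does the 28-day bullet reach this cohort as written?** Its two conditions are being enrolled and having no Safety Follow-up Visit. Protocol 12.2 bases the cohort's summaries on its enrolled subjects, and Section 8 of the SAP defines enrolment by consent and an enrolment date. Section 8.1.1.2 and Table 3-2 show that the cohort has no such visit. Both conditions are met.

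**Step 2: does a narrower reading remove the conflict?** Suppose the 28-day bullet is meant for the Treatment Cohort only. The Observational Cohort then falls under the first bullet, where its note sits, and that bullet ends at a visit the cohort never has. Neither bullet yields the last telephone contact as the end point.

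**Step 3: days of collection left after Study 110 Day 1 under the literal rule.** The formula is max(0, 28 − days from last dose to Day 1). The last-dose timings come from Section 9.1. Visits are taken on their nominal days, with Day 1 on the same day as Week 24 (Study 109) or Week 26 (Study 011B).

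| Child | Days since last dose | Days left |
|---|---|---|
| Study 109, last dose at the Week 24 visit | 0 | 28 − 0 = 28 |
| Study 109, last dose the evening before Week 24 | 1 | 28 − 1 = 27 |
| Study 011B, last dose the evening before Week 24 | 14 + 1 = 15 | 28 − 15 = 13 |
| Study 109, stopped after 4 weeks | 20 × 7 = 140 | 0 |
| Study 011B, stopped after 4 weeks | 22 × 7 = 154 | 0 |

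Any child whose last dose was 28 days or more before Day 1 has 0 days left. A later Day 1 at a site not yet activated shortens the non-zero figures further.

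**Step 4: compare with the stated follow-up.** Two years is 2 × 365.25 = 730.5 days. With the ± 4-week window on the final contact, the range is 730.5 − 28 = 702.5 to 730.5 + 28 = 758.5 days. The longest literal window is 28/730.5 = 3.8% of the intended period; the Study 011B window is 13/730.5 = 1.8%.

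**Step 5: compare with the first call.** Three to four months is 3 × 30.44 = 91 to 4 × 30.44 = 122 days. Whether that is counted from the last dose or from Day 1, it falls after the 28-day cut-off. Under the literal rule, every scheduled contact after Day 1 lies outside the collection window.

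**The case against.** The best case for the plan is that the intent is clear and the 28-day bullet was never meant for this cohort.

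- The bullet counts from the last dose of study drug, and these children receive none in Study 110 (Sections 10.2 and 10.3). Where the protocol means dosing in the previous study, Section 8.1 says so.
- The bullet has an obvious target in Treatment Cohort children without the visit, such as those moving directly to commercial drug (Section 8.1.1.3). Its 28 days match the treatment-emergent window in Section 12.3.
- The literal reading gives zero days to early discontinuers, whom Section 9.1 expressly admits to this cohort.
- Section 13.1.1.3 also has all subjects asked about events at each study visit, and Section 8.1.3 counts telephone contacts as study visits.
- The follow-up visit in 13.1.2.2 can refer to this cohort's calls, which Section 12.4.2.1 labels long-term follow-up visits. The related-only rule there starts after the study concludes. Section 13.1.2.3 requires notification of SAEs within 24 hours whatever the presumed relationship, with no 28-day limit.
- Section 11.7.1 refers to separate completion guidelines and training, which may settle the matter for sites.

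Most of this stands as evidence of intent. It defeats the stronger inference a reader might draw, that the 2-year SAE endpoint is in fact cut to between 0 and 28 days: Table 3-2 and SAP Table 13-3 expressly keep collection open to the last call. It also means 13.1.2.2 is ambiguous for this cohort rather than plainly wrong. It does not cure 13.1.1.3, which has no cohort exception and, as Step 2 shows, gives the cohort no workable end point even on the narrower reading.

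**Conclusion.** The contradiction is real and should be corrected. Section 13.1.1.3 as written conflicts with Table 3-2, Sections 8.1 and 8.1.2.2, and SAP Table 13-3 on the collection window for the cohort's only endpoint. At a site that applied the 28-day bullet, at most 3.8% of the intended window would remain, and nothing for children who stopped drug early.

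These figures depend on that literal reading and on nominal visit days. Nothing in the documents shows that any site applied it, and they give no size for the Observational Cohort, so the number of SAEs at risk cannot be estimated. What is established is a risk of uneven ascertainment, not a lost endpoint. Severity is moderate: the objective is secondary, the cohort is untreated, the output is descriptive, and the primary endpoint is unaffected.

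**What to change.** Limit the 28-day bullet in 13.1.1.3 to the Treatment Cohort. Add that for the Observational Cohort all SAEs, regardless of causality, are collected from consent through the last telephone contact at about 2 years, as in Table 3-2. In 13.1.2.2, clarify that the follow-up visit means the last telephone contact for this cohort.

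The cost is about two sentences in a protocol amendment or site clarification letter, with no new visits or data items. SAP Table 13-3 already agrees and needs no change. If follow-up has already ended, check the SAE reporting end dates by site before database lock, so that any uneven follow-up can be described alongside the SAE output.

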13.1.1.4 Adverse Event Severity

The investigator will determine and record the severity of all serious and non-serious AEs. The guidance available at the following website will be consulted: Common Terminology Criteria for Adverse Events (CTCAE), Version 4.0, Cancer Therapy Evaluation Program, http://ctep.cancer.gov/protocolDevelopment/electronic_applications/ctc.htm (Accessed August 2012). AEs of CTCAE Grades 4 and 5 will be documented as “life-threatening.” In considering the severity of an AE in a pediatric subject, the investigator will consider that reference ranges for pediatric clinical laboratory parameters may differ from those given in the CTCAE. The severity of an AE that does not appear in the CTCAE will be determined according to the definitions in [Table 13-1](#).

Table 13-1 Grading of AE Severity

Classification	Definition
Mild (Grade 1)	Mild level of discomfort and does not interfere with regular activities
Moderate (Grade 2)	Moderate level of discomfort and significantly interferes with regular activities
Severe (Grade 3)	Significant level of discomfort and prevents regular activities
Life-threatening (Grade 4)	Any adverse drug experience that places the subject, in the view of the investigator, at immediate risk of death

